**Specific Aim 1.** Conduct a cluster-randomized trial that includes 36 primary care clinics (34 randomized clinic units, with 3 clinics randomized together due to shared providers) with approximately 300 PCPs and more than 153,000 patients to one of three study arms: (a) PCP-Focused Group: PCP intervention using an EHR-linked, Web-based CP-CDS system, (b) shared decision-making tools (SDMT) Focused Group: PCP intervention using an EHR-linked, Web-based CP-CDS system including additional, or (c) usual care (UC) to assess whether this intervention can improve the delivery of evidence-based, personalized primary and secondary cancer preventive care in rural primary care settings. Specifically, the PCP-focused group will receive a point of care CP-CDS tool that is integrated into the EHR. The CP-CDS provides evidenced-based recommendations to the provider and patient related to overdue cancer prevention screening services and eligible for smoking cessation and obesity management referrals. The SDMT-focused group will also receive the CP-CDS. Furthermore, the SDMT-focused arm provides SDMT to the patient and provider at the time of the visit. The UC arm will not receive the CP-CDS or SDMT but will receive usual best practice advisory suggestions for cancer prevention screening and other usual care.

**Hypothesis 1 (H1).** Eligible study subjects will have significantly different rates of appropriate screening tests for breast, colorectal, and cervical cancer as defined by the U.S. Preventive Services Task Force (USPSTF) during the 12 months after the index visit by study arm, with PCP-focused group higher than UC and SDMT-focused group higher than UC.

**Hypothesis 2 (H2).** Eligible study subjects will have significantly different rates of human papilloma virus (HPV) vaccination in appropriate cases, as defined by the Advisory Committee on Immunization Practices/Centers for Disease Control and Prevention during the 12 months after the index visit by study arm, with PCP-focused group higher than UC and SDMT-focused group higher than UC.

**Specific Aim 2.** Assess the cost of the CP-CDS intervention from the health system perspective through measurement of healthcare utilization and use of diagnostic codes and billing levels related to cancer prevention services.

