#### **4.7 Definition and Measurement of Dependent Variables**

We will use a mixed-methods approach to determine the facilitators and barriers for achieving the specific aims. Appendix A contains the definitions, sources, and metrics for study variables.

**Cancer Screening Tests (Aim 1, H1):** The dependent variable for H1 is a binary variable indicating that the patient is up to date on the specific constellation of screening tests for breast, cervical, lung and colorectal cancer that were due at the index visit for the patient by 12 months after the index visit. Secondary endpoints for H1 will look at the same individual screenings, within 12 months of the index visit. Each patient will be classified as up to date or not (composite endpoint) on all appropriate screening tests, depending on sex, age, risk factors, and date of last needed screening tests according to active USPSTF recommendation statements. This variable will be based on EHR-captured procedure codes that are routinely gathered by the Wizard interface at actual and re-run visits, which manually force the capture of this data into the Wizard repository, and data will be obtained from the index visit date through 12 months past the last patient index date.

**HPV Vaccination Rates (Aim 1, H2):** New CDC recommendations put into effect at Essentia Health January, 2017 are reflected in changes to the HPV vaccination sample and recommendations in this study. Children ages 9-14 are now recommended to receive 2 HPV vaccine doses, while 3 HPV vaccine doses are still recommended for adolescents and young adults ages 15-26. The dependent variable for H2 is a binary variable indicating that the patient has had all 2 or 3 HPV vaccinations recommended by ACIP/CDC, dependent on age group, within 12 months of the index visit. This variable will be coded as "1" for patients having all 2 or 3 vaccinations and "0" for patients with 0-2 vaccinations, dependent on age group. HPV vaccination data will be obtained from the EHR from the index visit date through 12 months past the last patient index date.

**12-month Health Care Costs (Aim 2, H3):** Costs for this analysis are defined as intervention costs as well as the incremental medical care costs associated with the intervention from the health system

perspective.

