**Dependent Variables for Secondary Analyses:** In Appendix A, primary and secondary dependent variables are defined, some of which assess potential moderators of intervention effects. Secondary analyses include (a) rural-urban comparisons, (b) separate binary outcomes for the 3 screenings tested as a composite in H1: colorectal, breast, and cervical cancer, (c) lung cancer screening, (d) a binary outcome of any HPV vaccinations vs. none within 12 months of the index date, and (e) binary indicators for referrals to internal or community programs for , smoking cessation, or medications prescribed for smoking cessation, (f) smoking cessation by 12 months following the index date.

**4.8 Measurement of Independent Variables Primary Predictor:** The primary predictor is the treatment arm to which a clinic is randomized. This variable will be coded as a two degree of freedom contrast with the usual care (UC) arm as the reference category. Planned contrasts will examine pairwise differences in treatment arms. **Patient and Provider Characteristics:** Patient and provider characteristics listed in Appendix A will be documented so we can assess the extent to which results apply to subgroups of patients or whether patient or PCP characteristics modify intervention efficacy. Patient sex will be an important covariate and stratifying factor in the analysis because screening rates for H1 are likely to be different by sex. Clinic randomization may introduce random or selection-induced patient or PCP covariate imbalance, necessitating adjustment. Patient characteristics obtained from the EHR, include demographics, pre-intervention comorbidities (derived from dated ICD-10 diagnosis codes), insurance status, smoking status, among others. Furthermore, primary care visit dates will link patients and PCPs. We will have complete data for PCP characteristics, including age, sex, race, ethnicity, physician or allied provider (i.e., nurse practitioner), department.

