## 4.9 Analysis Plan

### 4.9.1 Aim 1 Analytic Approach

Hypotheses 1 & 2 in Aim 1 posit that patients seen at clinics with the SDMT-focused or PCP-focused cancer screening CDS will be more likely than patients seen at UC clinics without the CDS to have appropriate screening for breast, cervical, and colon cancer (H1), and a full course of three HPV vaccinations (H2) within 12 months of an index visit. Because clinics are the unit of randomization and the outcome varies at the level of the patient, generalized linear mixed-model regression with a logit link and binomial error distribution will be used to test the effect of the interventions. The general form of the analytic model for H1 & H2 is:

$$\text{Dependent Variable}_{kji} = \gamma_{00} + \gamma_{100}\text{SDMT\_CDS}_k + \gamma_{200}\text{PCP\_CDS}_k + \gamma_{001}\text{SEX}_i + [\nu_{k00} + u_{kji} + e_{kji}]$$

The dependent variable in each model is a binary indicator of appropriate screening (H1) or complete course of HPV vaccination (H2). The dependent variable is predicted by the two fixed-effect terms representing the study arm contrast (SDMT\_CDS and PCP\_CDS). Patient sex is included as a fixed effect because screening rates for H1 and vaccination rates for H2 are likely to be different. We will screen patient characteristics to determine

whether they differ across study arm and include patient covariates in the model when they are unbalanced by treatment arm. Random terms are included for clinic ( $v_{k00}$ ), provider ( $u_{kj0}$ ), and patient ( $e_{kii}$ ). The provider random term will be removed if the provider intra-cluster correlation (ICC) is less than 0.005. A significant treatment group effect ( $P<0.025$ ) and positive and significant parameters for the treatment group terms  $\gamma_{100}$  and  $\gamma_{200}$  for each hypothesis will support the H1 & H2 predictions that clinics with CDS interventions are more effective than clinics without them for increasing cancer screening and HPV vaccination rates. This model will include patient sex and patient variables unbalanced by study arm as well as the indicated random effects. Treatment group heterogeneity by sex will be assessed by including interaction terms between patient sex and the two study arm indicators.

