## Appendix A. List of Dependent and Independent Variables.

Figure A.1. Variables for Analysis including Description, Data Source, and Classification. ICD-9 diagnosis codes will be replaced with ICD-10 diagnosis codes in 2015. Blue shaded variables are CFIR related metrics

Variable	Description	Data Source	Variable Classification
Dependent Variables			
Up-To-Date Cancer Screening	A binary variable indicating the patient is up to date on screening tests for breast, cervix, and colorectal cancer by 12 months following the index visit.	EHR Procedure Results from Wizard re-run	Binary
Up-To-Date Colorectal Cancer Screening	A binary variable indicating the patient is up to date on colorectal cancer screening by 12 months following the index visit.	EHR Procedure Results from Wizard re-run	Binary
Up-To-Date Breast Cancer Screening	A binary variable indicating the patient is up to date on breast cancer screening by 12 months following the index visit.	EHR Procedure Results from Wizard re-run	Binary
Up-To-Date Cervical Cancer Screening	A binary variable indicating the patient is up to date on cervical cancer screening by 12 months following the index visit.	EHR Procedure Results from Wizard re-run	Binary
All HPV Vaccinations Complete, age 18-26	A binary variable indicating the patient has had all HPV vaccinations as recommended by ACIP/CDC within 12 months of the index visit.	EHR Procedure Results from Wizard re-run	Binary
Some HPV Vaccinations Complete, age 18-26	A binary variable indicating the patient has had at least 1 HPV vaccination as recommended by ACIP/CDC within 12 months of the index visit.	EHR Procedure Results from Wizard re-run	Binary
All HPV Vaccinations Complete, age 9-17	A binary variable indicating the patient has had all HPV vaccinations as recommended by ACIP/CDC within 12 months of the index visit.	EHR Procedure Results	Binary
Lung cancer screening	A binary variable indicating the patient is up to date on lung cancer screening by 12 month following the index visit.	EHR Procedure Results from Wizard re-run	Binary
Any quit attempts	A binary variable indicating that the patient made any smoking quit attempts in the 12 months following the index date	Wizard EHR	Binary
Smoking status at 12 months	A binary variable indicating that the patient has a non-smoker smoking status at 12 months following the index date	Wizard EHR	Binary

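### Section 4.7 puts lung screening into the H1 composite, while every other place that states the H1 components uses breast, cervical and colorectal screening only

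*Combined protocol and SAP*

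**What the plan says.** All references are to the combined protocol and SAP. Section 4.7, in the paragraph headed Cancer Screening Tests (Aim 1, H1), makes the H1 outcome a binary indicator, assessed at 12 months, of being "up to date on the specific constellation of screening tests for breast, cervical, lung and colorectal cancer that were due at the index visit". The opening paragraph of the same section states that "Appendix A contains the definitions, sources, and metrics for study variables".

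Appendix A, Figure A.1, defines the composite as the patient being "up to date on screening tests for breast, cervix, and colorectal cancer by 12 months following the index visit". A separate row covers lung: "the patient is up to date on lung cancer screening by 12 month following the index visit". Later in 4.7, the list of secondary analyses gives "separate binary outcomes for the 3 screenings tested as a composite in H1: colorectal, breast, and cervical cancer, (c) lung cancer screening".

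Hypothesis 1 in the Specific Aims and the analytic approach in 4.9.1 both name three cancers and omit lung. Section 4.9.2 sizes H1 on women not up to date on three screens and on men not up to date on colon screening alone. Section 4.9.6 names colorectal, breast and cervix as the parts of the H1 endpoint and adds lung as a further outcome.

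**The concern.** H1 is the first hypothesis of Aim 1, and the sentence that sets out to define its outcome describes a different endpoint from the one hypothesised, modelled and sized. The rest of that paragraph does not correct it. It classifies patients on all tests appropriate to their sex, age and risk factors, and that wording can also cover lung. No statement says which section prevails.

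An analyst who programs from 4.7 and one who programs from Appendix A would score some patients in opposite ways. If the difference were noticed only after results by arm were known, whichever definition was then chosen would be open to challenge.

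**Working it through.** **1. The places that state the H1 components**

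| Place | H1 components | Lung |
|---|---|---|
| 4.7, H1 dependent variable | breast, cervical, lung, colorectal | inside the composite |
| Specific Aims, Hypothesis 1 | breast, colorectal, cervical | not mentioned |
| 4.7, secondary list | colorectal, breast, cervical (called three screenings) | separate item (c) |
| 4.9.1 | breast, cervical, colon | not mentioned |
| 4.9.2 | women: three screens; men: colon only | not mentioned |
| 4.9.6 | colorectal, breast, cervix | additional outcome |
| Appendix A, Figure A.1 | breast, cervix, colorectal | own row |

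One place includes lung and six do not. Three of the six set lung apart expressly.

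**2. How the two definitions score a patient**

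| Due at index | Completed by 12 months | 4.7 read literally | Three-screen definition |
|---|---|---|---|
| colorectal | colorectal | success | success |
| colorectal and lung | both | success | success |
| colorectal and lung | colorectal only | failure | success |
| colorectal and lung | lung only or neither | failure | failure |
| lung only | either | could enter H1 | not in H1 |

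The outcome differs only for patients also due for lung who complete everything else. The denominator could differ for patients due only for lung, although 4.7 does not say that they are included.

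**3. What the H1 planning figures were built on**

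Inputs from 4.9.2: 33,264 women (11,088 per arm), 9,390 men (3,133 per arm), 10 clinics per arm, ICC 0.005 to 0.02. Sex-specific rates are from Table 2.

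- Patients per arm: 11,088 + 3,133 = 14,221, or 1,422.1 per clinic.
- Effective n = 14,221 / [1 + (1,422.1 − 1) × ICC]. At ICC 0.02: 14,221 / 29.42 = 483 (plan: 484). At ICC 0.005: 14,221 / 8.106 = 1,754 (plan: 1754).
- Pooled share up to date: (33,264 × 0.34 + 9,390 × 0.60) / 42,654 = 39.7% (plan: 40%).
- Pooled anticipated rates = (33,264 × F + 9,390 × M) / 42,654. UC (12%, 7%): 10.9%. PCP CDS (19%, 14%): 17.9%. SDMT CDS (25%, 20%): 23.9% (plan: 11, 18 and 24%).

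The counts and weights are three-screen counts and no lung figure enters. The note to Table 1 in section 2.3 says that lung was not assessed in the preliminary data. The match says nothing about where the sex-specific rates in Table 2 come from, because the plan gives no derivation for them.

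**4. Can an effect on power be derived?**

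Let p be the three-screen rate, L the share of patients also due for lung, and u the share of those who complete lung among patients who complete their other tests. Taking L to be the same among completers, the four-screen rate is p × (1 − L + L × u). The documents give neither L nor u, so the values below are assumptions, chosen only to see whether the direction is fixed. The planned difference is 18% − 11% = 7.0 points.

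- L = 0.02, u = 0.10 in both arms: 0.11 × 0.982 = 10.8%; 0.18 × 0.982 = 17.7%; difference 6.9 points.
- L = 0.15, u = 0.10 in both arms: 0.11 × 0.865 = 9.5%; 0.18 × 0.865 = 15.6%; difference 6.1 points.
- L = 0.15, u = 0.05 in UC and 0.50 in PCP CDS: 0.11 × 0.8575 = 9.4%; 0.18 × 0.925 = 16.7%; difference 7.2 points.

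The difference can shrink or grow depending on inputs that the plan does not contain.

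**The case against.** The strongest reply is that the documents largely settle the matter themselves. The secondary list in the same section counts three screenings in H1. Appendix A, to which 4.7 defers for definitions, has a three-screen composite and a separate lung row. The data request in Figure A.3 carries separate H1 and Lung eligibility flags and analyses the records separately. On this view one stray word remains.

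Much of that stands. Three screens is the evident reading, and the separate flags make it unlikely in practice that lung-only patients would be put into H1. But Figure A.3 does not list the H1 components, and the sentence that defines the outcome is still wrong as written.

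Four stronger readings are tempting and are not supported:

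- **That the trial loses power.** This needs lung eligibility and uptake figures that the documents do not give, and the direction can reverse.
- **That men in general move from one required test to two.** The 4.7 wording counts only tests due at the index visit, so this applies only to men also due for lung.
- **That reproducing the planning rates proves which endpoint was meant.** It shows only that the weights are three-screen counts.
- **That four screens were intended because the Introduction says lung was added back.** That text returns lung to the protocol's scope and does not say that it joins H1.

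**Conclusion.** The point holds as a mis-stated primary endpoint. One sentence in 4.7 conflicts with six other statements of the same composite, including one in its own section and one in the appendix it cites. The patients affected are those also due for lung screening who complete all their other due tests but not lung, plus any lung-only patients if the denominator were read literally. Their number cannot be obtained from the documents. A four-screen H1 has no stated planning basis. No loss of power is claimed. The conclusion rests on the text alone and needs none of the assumed values for lung eligibility or uptake. It should be fixed before the analysis.

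**What to change.** Before outcomes are examined by arm:

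- Delete lung from the H1 dependent variable in 4.7, so that it agrees with the secondary list in 4.7 and with Appendix A.
- Add one sentence saying that patients due only for lung screening are outside the H1 denominator, consistent with the separate H1 and Lung flags in Figure A.3.
- Keep lung screening as the separate secondary outcome.
- Record the decision with its date.

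The cost is one word removed, one sentence added and a dated note, with no new data or sample size work.

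If four screens are intended instead, revise Hypothesis 1, the secondary list in 4.7, 4.9.1, 4.9.2, Table 2, 4.9.6 and Appendix A to match. That option needs new planning rates. It also needs a rule for which index date applies when a patient has separate H1 and Lung records, because Figure A.3 notes that these dates can differ.

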**Hypothesis 3 (H3).** After controlling for demographics and baseline clinical risk factors, eligible study subjects will have significantly different overall healthcare costs during the 12 months after the index visit by study arm, with PCP-focused and SDMT-focused arms higher than the UC arm.

**Hypothesis 4 (H4).** After controlling for demographics and baseline clinical risk factors, eligible study subjects will have significantly different frequencies of diagnostic codes related to cancer prevention services and billing levels in the 12 months after the index visit by study arm, with PCP-focused and SDMT-focused arms higher than the UC arm.

**Specific Aim 3.** Describe critical facilitators and barriers for the CP-CDS implementation process, outcomes, and future dissemination strategies using a mixed-methods approach supported by the CFIR and RE-AIM conceptual frameworks.

Results of this pioneering project will: (a) lead to improved delivery of personalized, evidence-based primary and secondary cancer preventive services, helping achieve Healthy People 2020 goals; (b) advance our understanding of how best to integrate effective personalized cancer preventive CDS into primary care workflows; and (c) guide effective dissemination and implementation of similar EHR-linked, Web-based, personalized CDS systems to other rural primary care clinics and delivery systems.

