Intervention costs include CDS implementation and maintenance, training, and incentives but exclude intervention research and development costs. Medical care costs include costs of all medical services-including laboratory, physician services, and screening tests-incurred in the 12-month post-index date period by participants in each study group, as indicated by EH billing and clinical encounter data. Described in detail in the Section 4.9.3 below, we will use relative value units (RVUs) and diagnosis-related groups (DRG) to calculate inpatient and outpatient costs for patients randomly assigned to each study group and standard accounting methods to measure the cost of the CP-CDS intervention. Emergency visits and hospitalizations may be too infrequent in the study sample to accurately predict a population-wide impact of the study interventions. If there were no intervention impact on these utilization components during the study period, including their costs would substantially increase variance in the cost data without adding to the accuracy of the cost assessment. Therefore, we will first assess whether there is a differential impact between CP-CDS and usual care on use of these services and will include their costs only if a difference is observed. Reliance on EH billing records for measuring medical care use may miss costs incurred in other health systems; however, this opportunity is expected to be equal across randomized study arms, and cross-system medical utilization is expected to be relatively limited in the primarily rural study population.

While market prices generally are a good estimate of the costs for medical services, the paid amount in this claims system is specific to HealthPartners at a particular time and may provide a biased view of costs between pre- and post-intervention periods. To address this, we will use Total Care Relative Resource Values™ (TCRRVs), which are a nationally standardized set of measures that have been endorsed by the National Quality Forum and are derived from Centers for Medicare and Medicaid Services (CMS) relative value units (RVUs). TCRRVs extend CMS RVU measures to include utilization categories, such as laboratory services and medications, which do not have CMS RVU weights. Specifically, TCCRVs defined during the midpoint of patient accrual and follow-up (e.g., 2019) will be used to convert claims to represent U.S. dollars.

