#### 4.9.3 Aim 2 Analytic Approach

**12-Month Utilization (H3):** Incremental medical costs will be estimated using standard health econometric methods. A generalized estimating equation (typically assuming a gamma distribution and log link function) will be used to estimate costs by study arm while allowing clustering by clinic and controlling for demographics and baseline clinical risk factors. The marginal effect of being assigned to an intervention clinic will provide an estimate of the incremental medical cost associated with the CP-CDS intervention. Urban and rural clinic- based eligible subjects receiving care from eligible PCPs will also be

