**Table 3. Anticipated pattern of effects for H2 (receipt of 3 HPV vaccinations)**

UC	20% (30% F, 10% M)
PCP CDS	33% (45% F, 20% M)
SDMT CDS	40% (55% F, 25% M)

compared. The estimates assume that the CP-CDS is implemented in a large health plan with an EHR capable of exporting data to Web-based clinical algorithms. Implementation in settings without this capability would likely incur additional costs.

**12-Month Diagnostic and Billing Codes (H4):** Similar to costs, a generalized estimating equation with a time  $\times$  study group interaction term will be used to estimate use rates of diagnostic and billing codes for cancer preventive services or the encounter billing level by study arm while allowing for clustering by clinic and controlling for demographics and baseline clinical risk factors. The marginal effect of being assigned to an intervention clinic will provide an estimate of the incremental effect associated with the intervention. All statistical comparisons will be 2-sided. P-values of less than .05 will be considered statistically significant.

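### The H3 cost outcome is chosen by whether emergency and hospital use differs between arms in the trial's own data; it should be fixed in advance.

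*Combined protocol and SAP*

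**What the plan says.** Hypothesis 3 in the Specific Aims is about total cost: "eligible study subjects will have significantly different overall healthcare costs during the 12 months after the index visit by study arm", with both CDS arms expected to be higher than usual care. Section 4.7 (12-month Health Care Costs) starts in line with that. "Medical care costs include costs of all medical services", and for the costing "we will use relative value units (RVUs) and diagnosis-related groups (DRG) to calculate inpatient and outpatient costs".

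The same paragraph then makes an exception. It notes that "Emergency visits and hospitalizations may be too infrequent in the study sample to accurately predict a population-wide impact of the study interventions", and argues that if there is no effect on these services, counting their costs adds variance and no accuracy. It concludes that "we will first assess whether there is a differential impact between CP-CDS and usual care on use of these services" and that the team "will include their costs only if a difference is observed".

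Section 4.9.3 gives the H3 analysis: "A generalized estimating equation (typically assuming a gamma distribution and log link function) will be used to estimate costs by study arm", allowing for clustering by clinic and controlling for demographics and baseline risk. The significance rule closes that section: "All statistical comparisons will be 2-sided. P-values of less than .05 will be considered statistically significant". Neither statement mentions the preliminary comparison. Figure A.1 lists no cost outcome, and Figure A.3 leaves the cost fields to data-dictionary tabs that are not part of the documents.

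**The concern.** Which outcome H3 tests is known only after the arms have been compared on a component of that outcome. Use of emergency and hospital services is strongly related to their cost. Costs that enter because use differed therefore tend to enter when their own arm difference is large by chance. The model's p-value and interval are computed as if the outcome had been fixed.

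The rule also treats not seeing a difference as evidence of no effect, although section 4.7 itself doubts that these events are frequent enough to show one. When the costs are left out, the result describes a narrower quantity than the overall cost that H3 names.

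The visible text gives no test, threshold or model for the first comparison, and no commitment to report the version not chosen. The two-sided .05 rule could be read as the criterion, but the selection problem is the same on that reading.

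**Working it through.** **Starting point.** The documents give no variance, power or detectable difference for H3, so there is no plan figure to reproduce. The only stated number that bears on the point is the two-sided .05 level. All other values below are assumptions, with the first comparison at two-sided .05 unless noted.

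**1. No true effect, additive normal approximation.** Let U be the standardised arm difference in use and e, f independent standard normals.

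- Emergency/hospital cost difference: J = ρU + √(1−ρ²)·e
- Other cost difference: O = cJ + √(1−c²)·f
- r is the SD ratio of emergency/hospital cost to other cost.
- Rule: if |U| > 1.96, test (O + rJ)/√(1 + r² + 2cr); otherwise test O. Both are compared with 1.96.

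With 2,000,000 draws per cell, ρ from 0.5 to 0.9 and r from 0.5 to 5, the type I error per contrast is:

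| Component correlation c | Type I error |
|---|---|
| −0.3 | 4.9–7.4% |
| 0 | 5.1–7.6% |
| +0.3 | 5.2–7.4% |

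Mid-range (ρ = 0.7, r = 1 to 2) it is 5.3–6.1%. The limit, with total cost driven wholly by use and other cost independent, is 0.05 × 1 + 0.95 × 0.05 = 9.75%.

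A second parameterisation used emergency/hospital shares of cost variance of 0.3 to 0.9, ρ of 0.6 or 0.9, and c of 0 or 0.3. It gives 5.3–7.3% with a first threshold of .05, 5.4–8.1% with .10 and 5.5–8.5% with .20. With 11, 11 and 12 units and ρ = 0.9, the chance of at least one false positive over the two CDS-versus-usual-care contrasts rises from about 9.1% to 10.0–11.6% if the first comparison pools the CDS arms. It rises to 10.3–13.3% if a difference in either arm suffices.

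**2. True effect on the emergency/hospital component.** Let the true difference be d standard errors in both use and cost. Then

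- P(included) = Φ(d − 1.96) + Φ(−d − 1.96)
- Mean contribution = d·P + ρ[φ(1.96 − d) − φ(1.96 + d)]

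For d = 1, P = 0.1685 + 0.0015 = 0.170 and the bracket is 0.2516 − 0.0050 = 0.2466. At ρ = 1 the mean contribution is 0.170 + 0.247 = 0.417, that is, 58% shrinkage. When included, the mean is 0.417/0.170 = 2.45 times the truth. For ρ from 0.5 to 1:

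| d | Included | Average shrinkage | Overstatement when included |
|---|---|---|---|
| 1 | 17% | 58–71% | 72–145% |
| 2 | 52% | 28–38% | 19–39% |
| 3 | 85% | 7–11% | 5–9% |

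At d = 0 the mean is zero, so with no true difference there is no bias.

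**3. Patient-level check.** The model was a log-link GEE with arm as the only covariate, a clinic-level sandwich SE and t with 21 df. It compared 11 with 12 units at 38,053/34 = 1,119 patients per unit. The count comes from Figure A.3, whose file can list a patient more than once, so it is an upper figure. Assumed inputs were other cost with base 3,000; 0.10, 0.30 and 0.30 events per patient; and mean event cost 6,000, 8,000 and 15,000. Emergency/hospital care is then about 17%, 45% and 60% of total cost.

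- *No effect:* the rule rejects in 5.5%, 6.3% and 7.9% (5.2–5.5%, 6.2–6.6% and 7.8–8.4% over repeat runs), against 4.8–5.2% for either outcome fixed in advance. The figure near 5% needs a small-sample correction to the sandwich SE; without it, fixed outcomes reject in about 6%.
- *Use 12% lower:* the costs are included in 36–44% of trials. The true total log ratio is −0.020, −0.055 and −0.075; the mean under the rule is −0.011, −0.034 and −0.049. Shrinkage is 1 − 0.011/0.020 = 45%, 1 − 0.034/0.055 = 38% and 1 − 0.049/0.075 = 35%. When included, the mean is −0.035, −0.081 and −0.110, an overstatement of 46–70% before rounding. The 70% rests on about 0.36 × 2,750 = 990 trials; repeat runs put the top of the range at 59–64%.

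**The case against.** The rule is written down in advance with a variance rationale, so it is not a hidden choice. The error inflation is modest and disappears in some settings with negatively correlated components. The higher patient-level figures assume 0.30 events per patient, whereas section 4.7 expects few; a rarer-event case (0.03 per patient, mean cost 20,000, also assumed) gave 5.3%. The patient-level check has no covariates, and its use–cost correlation (0.88–0.95) is at the top of the assumed range. Bias needs a true effect on emergency or hospital use, and the documents predict none. CP-CDS versus usual care reads most naturally as a pooled comparison, and a criterion could exist in the data-dictionary tabs.

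Most of this stands and limits the size of the problem. It does not remove it. Announcing a data-dependent choice does not make a p-value that ignores it valid. A criterion in an unseen file would settle how the choice is made but leave the outcome selected by arm data. Section 4.7 also says these costs would substantially increase variance, so the documents cannot show that the small-effect case applies. If a difference meant any numerical difference, the costs would practically always enter and the sentence would serve no purpose.

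**Conclusion.** The concern holds. As written, H3 has no single cost outcome, and its test and interval ignore the step that selects one. Under the assumed values the error rate is about 5% to 8% per contrast, and 5.3–6.1% mid-range. The distortion of the estimate matters more: if use of these services truly differs, the overall cost effect is shrunk on average and overstated in the trials that include it.

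A related harm comes from leaving the costs out, not from the look: higher screening cost offset by lower acute-care cost would be missed. With a full offset and other cost raised by 1, 2 or 3 standard errors, a narrow outcome fixed in advance declares a difference in 17%, 52% and 85% of trials although overall cost is unchanged. That is why H3's wording must match the outcome. H1, H2 and H4 are unaffected.

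**What to change.** Delete the conditional sentence in section 4.7. In 4.7 and 4.9.3, name one H3 cost outcome before arm data are compared. Report the other version as a fixed secondary outcome, and the utilisation comparison with its model and interval, whatever they show. Total 12-month cost including emergency and inpatient care matches H3 as worded. If the team prefers the narrower outcome for precision, H3 should stop referring to overall costs. If the comparison has already been made, say so and present both versions side by side.

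The change is one of wording. Choosing total cost loses precision in dollars: with independent components its SE is √(1 + r²) times that of other cost, or 1.1, 1.4, 2.2, 3.2 and 5.1 times at r = 0.5, 1, 2, 3 and 5. On the log-ratio scale of the planned model the factor was 0.9, 0.9 and 1.6 in the three patient-level scenarios, though a given dollar difference is then a smaller ratio of a larger total. The fixed secondary outcome keeps the more precise comparison. Section 4.7 already plans DRG-based inpatient costing and Figure A.3 already plans 12-month utilisation data; the team should confirm that the emergency and inpatient fields are in the extract.
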